3.6.4 Procedural variations

During Phase I, we will also pilot two procedural variations at selected sites to determine the scalability of the intervention for Phase II. First, to account for the overrepresentation of some ethnic minorities in the study population, materials (including leaflets, questionnaires, participant information sheets etc.) will be available in both English and Urdu and the intervention delivered by a bilingual MHR at specific sites to allow PWMI with limited English to participate in the study.

3.7 Trusts and study sites

Three Trusts will be involved in phase I: Tees, Esk and Wear Valleys NHS Foundation Trust (TEWV –the largest mental health Trusts in England) will be the host Trust. TEWV has numerous sites across Yorkshire. Bradford District Care Trust (BDCT) will also include a minimum of two sites. TEWV and Bradford will recruit from secondary care. SHSC/Sheffield CCG will facilitate recruitment in primary care sites only. SHSC/Sheffield CCG will approach 2-3 primary care networks to participate in Phase I and increase this to

all (15) networks for Phase II. All trusts have substantial experience with facilitating stop smoking research and support infrastructure is already in place, having recently been involved in the successful delivery of the SCIMITAR+ trial [30].

3.8 Measures

3.8.1 Baseline measures

Baseline measures will be collected via a brief questionnaire and health records.

- *3.8.1.1 Socio-demographic characteristics:* These include age, sex, employment status, ethnicity, education, employment, accommodation type and marital status.
- 3.8.1.2 Smoking-related characteristics: These include general smoking characteristics, quit attempts and methods (including e-cigarettes), nicotine dependence [53], strength of urges to smoke (SUTS) [54], motivation to quit [55] and adexhaled breath carbon-monoxide (CO) reading.
- 3.8.1.3 General and mental health-related characteristics: These include most recent diagnosis (if available), antipsychotic medication use, and acute events (e.g. hospitalisation) in the last year. Mental health symptoms will be assessed with the PHQ-9 [56], GAD-7 [57] and SF-12 questionnaires [58].
- 3.8.1.4 Health behaviour characteristics: Alcohol use [59], exercise [60] and diet [61] will be assessed.

3.8.2 Primary outcome measures:

3.8.2.1 Feasibility and acceptability outcomes: The primary feasibility outcome measures in the feasibility trial will be consenting rate and recruitment frequency. Consenting rate will be calculated from the number of eligible participants approached who consent to take part in the study. The criterion to judge whether a large-scale RCT is feasible using the proposed recruitment approach is consenting a minimum of ~15% of eligible participants (see 3.14) which is slightly lower than the consenting rate typical in clinical trials in general patient populations in the UK [62]. Recruitment frequency will be calculated as the number of eligible patients at each site who agree to participate in the trial per month. Based on our projection of the number of participating trusts and sites in the full RCT, we would require around six participants per month from each Trust to deliver the full RCT successfully (see 3.9/4.4). MHR (or CPN) will be asked to record the number of non-eligible patients using a check list of common reasons for exclusions.

The acceptability of the intervention and research procedures will be investigated using a short proforma based on the Theoretical Framework of Intervention Acceptability [63], provided to all participants at follow-up. This will be complemented by qualitative interviews conducted with a sample of approximately 18 participants from the intervention and control group (including, wherever possible, those who disengaged during the course of the study). We will gain insights into patients' experience with the intervention and barriers to and facilitators of success, both in terms of the intervention content and the research process. MHR (or CPN) delivering the intervention in each Trust will provide detailed feedback on their experience, and on barriers and facilitators to

delivery, through feedback diaries and interviews; in addition, in-depth qualitative interviews will be conducted with six MHR/CPNs (two from each Trust).

The attrition rate will be measured as the number of participants who fail to complete follow-up at 1 month. In order to ensure a sufficiently robust effect estimate, which can be affected by high attrition rates in intention to treat analyses [64], attrition rates should not exceed 30%, typical for smoking cessation trials in this population [65] (see 3.14). Reasons for withdrawal will be obtained, where possible. In addition, adherence to treatment (e-cigarette use) will be assessed at 1-month follow up.

3.8.2.2 Clinical (smoking-related) outcomes: This is the primary clinical outcome measure for the feasibility trial, assessed at 1-month follow up. Continuous abstinence will be defined as not having smoked in the two weeks prior to follow-up (weeks 5 and 6 from enrolment), verified by a CO reading below 10 ppm, in keeping with the standard measure used in Stop Smoking Services. This measure will be used to determine whether to progress to Phase II and a full trial, based on the confidence interval approach (see 3.9 and 3.14).

3.8.3 Secondary outcome measures:

3.8.3.1 Feasibility and acceptability outcomes: Fidelity will be assessed by randomly sampling two intervention sessions per site with trained staff, audio-recording them and coding the use of behaviour change techniques (BCTs) delivered during the session to determine the proportion of BCTs used compared to specification in the manual [66]. Characteristics of 'usual care' in different locations will be also noted, recording two interactions of patients with CMHTs or GPs at each site at baseline and using short proforma with control group participants at follow-up. While the nature of the intervention and delivery format means that contamination is unlikely to be a problem, qualitative exploration will be undertaken with 25% of control group patients to investigate in depth reasons for smoking behaviour change and identifying potential (unintentional) links with our intervention. Based on our findings, we will estimate the presence/extent of contamination in the control group, and the need to change the study procedure (e.g. spacing randomisation per site). Further, the feasibility of intervention delivery via CPNs and using both English and Urdu will be assessed by calculating the number of successfully trained CPNs in each Trust, their recruitment rate and fidelity of intervention delivery as well as the proportion of Urdu speakers successfully recruited into the trial. Participant burden of data collection will be asssessed via qualitative interviews conduction online or via telephone with particpants to assess acceptability, which forms part of our list of measures collected in the feasibility study (Phase 1) to determine stop/go decision for the Phase 2 full trial. Should this issue be raised as a barrier to participation, we will seek to prioritise which measures to retain in the full trial.

3.8.3.2 Clinical (smoking-related) outcomes: Self-reported abstinence 2-4 weeks from enrolment or target quit date (whichever is later) will be recorded at 1-month follow-up. The change in cigarette consumption (and reduction in exhaled breath CO reading) from baseline to 1-month follow-up will be calculated in both intervention and control group participants.

3.8.3.3 Clinical (mental health-related) outcomes: At 1-month follow-up, general and mental health functioning will be assessed as per baseline (see 3.8.1.3).

3.8.3.4 Cost effectiveness: We will pilot service use questionnaires for health economic analysis and assess the health care utilisation data returned. We will calculate the costs of delivering the intervention and the control condition as the basis for the full RCT, for which a cost-effectiveness analysis is planned.

3.8.3.5 Serious Adverse Events (SAE): Adverse events (AE) will be recorded at 1-month follow-up as part of the follow-up questionnaires participants complete. The data management committee, led by a medical professional, will act as independent reviewer to determine whether any event is likely to be related to the trial and whether or not it is expected. This will include any events that may be related to the use of nicotine. Structured data on any events or 'side effects' experienced by participants will be collected at 1-month follow-up. In addition, we will also request Trusts to provide ad-hoc data on any serious adverse events that are disclosed through standard reporting procedures within the NHS, i.e. self-notification.

An event will be classed as serious if it considered to be: life threatening (i.e., event in which patient is at risk of death at the time of the event occurring); fatal; requiring unplanned admission to hospital resulting in an inpatient stay or extension of hospital stay beyond what is expected (i.e., patient operated on as an outpatient but remains in hospital overnight); resulting in persistent or substantial disability or incapacity; resulting in a congenital abnormality; or any other medical condition not listed here that might require medical or surgical intervention to prevent the above criteria occurring. Should the data management committee deem a serious adverse event to be related to the trial, this will be reported to the REC immediately (within the required 15 days).

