E-cigarettes are popular; in England use by smokers and recent ex-smokers currently stands at around 20% and around 30% used e-cigarettes in quit attempts in 2021, compared with 3% of smokers accessing SSS [31]. E-cigarette use is increasingly being recorded by SSS [32], and appeal in particular to PWMI who are more likely to have tried e-cigarettes and be current users than smokers in the general population [33]. There are several reasons for this. Firstly, e-cigarettes are relatively cheap compared with both cigarettes and other cessation treatment [34]. Second, they offer a simple stand-alone treatment that is intuitive to use. Third, since e-cigarettes simulate the sensory input from cigarettes and allow users to control the dose (unlike most NRT), they may appeal to more dependent smokers who have hitherto struggled to quit, with the potential to enhance existing cessation treatments and replace combustible tobacco products [35]. Thus e-cigarettes may be one solution to reduce smoking and encourage cessation in mental health care settings by functioning as a safer alternative to cigarettes [36].

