3.6.3 Procedure

Participants from Mental Health Trusts (Secondary Care) will be identified via health records prior to attendance at an up-and-coming appointment. A list of potential participants will either be checked for smoking status by clinical studies officers (CSOs) or a care coordinator/other appointed person at a GP surgery for primary care. Participants who smoke will then be contacted by letter containing the participant information sheet in advance of their appointment to ascertain interest in the study and may also receive a follow-up call to check they have received the letter. Those who are interested will be asked to respond to indicate this either verbally over the telephone, by advice slip in the post or using an online link. They will then receive a call from the research team to check eligibility using the checklist and answer questions which participants have relating to the study. If interest in participation is confirmed informed consent will be sent electronically (pathway 1). There will also be a paper-based option available for those who do not wish to use the electronic option. In this case, participant information and consent forms will be given in person at a scheduled appointment.

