Based on latest figures, it is estimated that involvement of two sites per Trust would reach around 100 patients per month per Trust. With smoking prevalence higher in this than in the general population, at around 40%, and with a conservative estimate of a consenting rate of around 15%, we therefore anticipate around six participants per Trust per month to be included in the feasibility trial, resulting in a total recruitment time of four months, with an additional month added as a buffer to account for uncertainty around the recruitment rate.

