3.13 Funding review

After Phase I, the outcome measures for the feasibility trial will be analysed and discussed with YCR regarding the feasibility of a fully powered RCT during the regular YCR KPI meetings as part of the award monitoring process. Following the feasibility trial, we request a formal "stop/go" point, and further funding for the full RCT will be determined based upon Phase I. A decision as to whether the project should progress to full trial stage will be made based on the following criteria:

a) Recruitment rate of six eligible participants per Trust with two study sites; b) Based on the confidence interval approach, an estimated effect that is larger than zero; c) Consent rate of ~15% of eligible participants, with no more than 30% attrition at follow-up; d) A clear indication of acceptability of the intervention and research process, based on qualitative and quantitative feedback measures collected from participants and research and CHMT staff (including proportion of participants from whom validated biochemical outcome measure (CO) could be successfully collected and successful training of CPN staff

to aid intervention delivery); e) Successful engagement with all co-applicant mental health Trusts for the main trial, with agreement to participate.

At this point, it may be necessary to recommend amendments to the study design/procedure to increase the chances of success of the RCT (see 3.13) and an updated sample size calculation will be conducted.

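### The 15% consent rate is a share of eligible patients at stop/go but a share of all smokers in the recruitment projection, and eligibility is not established for patients who do not reply

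*Protocol*

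**What the plan says.** Protocol 3.8.2.1 makes consenting rate one of two primary feasibility outcomes: "Consenting rate will be calculated from the number of eligible participants approached who consent to take part in the study". It sets the minimum at about 15%, and the funding review in 3.13 repeats this as criterion (c): "Consent rate of ~15% of eligible participants, with no more than 30% attrition at follow-up". Criterion (a) of the same list is a recruitment rate of six per Trust with two sites.

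The recruitment projection closing 3.9 starts from the estimate that "involvement of two sites per Trust would reach around 100 patients per month per Trust". It then takes smoking prevalence "at around 40%, and with a conservative estimate of a consenting rate of around 15" per cent, and arrives at six per Trust per month and four months of recruitment, with a fifth month as buffer. No step in that chain removes ineligible smokers.

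Section 3.6.1 excludes smokers who vape at least weekly, were inpatients in the last three months, are treated for drug or alcohol problems, have dementia, are pregnant or breastfeeding, or are in another cessation trial. It also requires capacity and willingness to quit or cut down.

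Section 3.6.3 sends letters to patients identified as smokers. Of those who reply with interest it says: "They will then receive a call from the research team to check eligibility using the checklist". The flow chart instead mentions screening of records before visits and an eligibility check on the appointment day.

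**The concern.** The same 15% is attached to two different populations. If 15% of eligible patients consent, criterion (c) is met, but the yield is six per Trust per month only when every smoker is eligible. Given the exclusions in 3.6.1, that will not be so. The six per month carries the Phase I timetable, and 4.4 derives the Phase II rate from it.

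The stated denominator is also hard to count. A patient who never answers the letter is not taken through the checklist. Records can settle some criteria for that patient, such as a recent admission, but not willingness to address smoking, and probably not weekly vaping. Sites could therefore count as eligible and approached either all smokers not ruled out by records, or only those who replied and passed the checklist. The second group has largely volunteered already, so its rate would be higher and would say little about recruitment yield.

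**Working it through.** **Inputs.** From 3.9: 100 patients reached per Trust per month with two sites, 40% smokers, 15% consent, 72 participants. From 3.7: three Trusts. From 4.4 and 4.8: 740 participants, three sites per Trust, 19 months planned and 22 with buffer. Five Trusts for Phase II is the three existing ones plus the minimum of two more in 4.4. The eligible share of smokers, e, is not in the protocol. I assume 0.9, 0.8 and 0.7.

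**The plan's own figures.** 100 x 0.40 x 0.15 = 6.0 per Trust per month, and 72 / (3 x 6) = 4.0 months. Both reproduce exactly, with e = 1.

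**With 15% of eligible patients, as in 3.8.2.1 and 3.13.**

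- Yield per Trust per month: 100 x 0.40 x e x 0.15 = 6e.
- Phase I months: 72 / (3 x 6e) = 72 / (18e).
- Phase II: six per two sites scales to nine per three sites, so five Trusts yield 5 x 9e = 45e per month, and the duration is 740 / (45e).
- Consent among eligible patients needed for six per month: 0.15 / e.

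| Eligible share e (assumed) | Per Trust per month | Phase I, months | Phase II, months | Consent needed for six |
|---|---|---|---|---|
| 1.0 (implicit in 3.9) | 6.0 | 4.0 | 16.4 | 15.0% |
| 0.9 | 5.4 | 4.4 | 18.3 | 16.7% |
| 0.8 | 4.8 | 5.0 | 20.6 | 18.8% |
| 0.7 | 4.2 | 5.7 | 23.5 | 21.4% |

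**Break-even points.** Phase I fits its five months when 72 / (18e) is at most 5, that is e of at least 0.80. Phase II fits 19 months when e is at least 740 / (45 x 19) = 0.87, and 22 months when e is at least 740 / (45 x 22) = 0.75.

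**Effect of the counting rule.** These inputs are illustrative only. Suppose 40 smokers are invited, 20% reply (8), 80% of these are eligible (6.4) and 50% of those consent (3.2).

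- Over checked-eligible responders: 3.2 / 6.4 = 50%.
- Over all eligible smokers invited, if 80% of non-responders are eligible too: 3.2 / 32 = 10%.
- Over all smokers invited: 3.2 / 40 = 8%.

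The same month passes a 15% threshold on the first count and fails it on the other two.

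**The case against.** **Recruitment is judged separately.** Recruitment frequency is the other primary feasibility outcome and is criterion (a) in 3.13. A reader might infer that the trial could be waved through on consent while recruitment fails. The protocol does not support that, because a shortfall against six per Trust would be visible. This stands, and it limits the harm. Criterion (a) does omit the per-month unit used in 3.8.2.1 and 3.9, which should be restored.

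**The denominator is not wholly unobservable.** The flow chart has records screened in advance, 3.6.1 documents reasons for exclusion and non-participation where possible, and 3.8.2.1 has staff count non-eligible patients. This stands for criteria held in records. It does not reach willingness to address smoking among patients who never reply. Nor does 3.8.2.1 say that only checked responders count. That is one reading the wording allows, and nothing in the protocol shows that the rate must exceed 15%.

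**The excluded share is unknown.** A reader might take 20% from the Background, where "in England use by smokers and recent ex-smokers currently stands at around 20" per cent. That figure includes recent ex-smokers and sets no frequency of use, whereas 3.6.1 excludes smokers who vape at least weekly. It cannot serve as the protocol's estimate of ineligibility.

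**Phase II has slack.** A reader might deduct exclusions from the eight per Trust in 4.4 and find an overrun at 20% ineligible: 740 / (5 x 8 x 0.8) = 23.1 months. But 15% of all smokers at three sites gives nine, so eight already carries an allowance of about 11% (1 - 8/9). On the proper base the figure is 20.6 months, inside 22. Five Trusts is also a minimum, and 3.7 expands the Sheffield networks from 2-3 to 15 in Phase II.

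**Conclusion.** The inconsistency is firm. The threshold in 3.8.2.1 and 3.13 concerns eligible participants, the projection in 3.9 concerns all smokers reached, and the two agree only at e = 1. For any lower share, meeting the threshold exactly yields fewer than six per Trust per month.

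The size rests on an assumed e. At 0.9 the cost is about half a month in Phase I. At 0.8 both phases draw on their buffers and still finish in time. At 0.7 both overrun. These figures also take the 100 patients per month and 40% prevalence as given, and assume yield proportional to the number of sites.

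That eligibility of non-responders is at best partly known follows from 3.6.3. How far this would inflate the rate depends on the counting rule, which the protocol leaves open.

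The consequence is an ambiguous consent criterion that says little about yield, and an optimistic recruitment figure. It is not a demonstrated wrong decision to proceed. The point is worth correcting because the threshold feeds a stop/go decision and the remedy is cheap.

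**What to change.** Settle the denominator before any stop/go data are seen, so that the result cannot choose the rule.

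1. Preferred: define the progression consent rate as participants randomised divided by smokers sent an invitation. This matches 3.9 and can be counted for everyone. State openly that 15% on this basis is stricter than 15% of eligible patients (equivalent to 18.8% of eligible if e = 0.8).
2. Alternative: keep 15% of eligible patients, say how non-responders of unknown eligibility are counted, and restate the projection to match.
3. Either way, report invited, responded, assessed, eligible and consented separately. Under option 1, consent among checked-eligible responders is descriptive, with no threshold.
4. Add an explicit eligibility fraction to the projections in 3.9 and 4.4 and restate the monthly figures, with a range.
5. Reconcile the timing of the eligibility check between the flow chart and 3.6.3, and add the per-month unit to criterion (a) in 3.13.

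The cost is wording and counts from the invitation and screening lists. The stated recruitment figure becomes somewhat less favourable. Under option 1, 15% of the projected 40 smokers is six per month, so criteria (a) and (c) would largely coincide unless the number of smokers reached differs from the projection.
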